# Tracking Physical Activity for Chronic Pain Management Among Older Adults in Detroit

## A. Background and Rationale

Improving function by increasing daily activity is a key goal of cognitive behavioral therapy (CBT) for pain. Incorporating wearable physical activity monitors into the design of cognitive behavioral pain self-management programs provides just-in-time data on patient progress that can be used to individualize behavioral messages and inform goal-setting. The 2016 National Pain Strategy encourages the use of wearable monitors as a pain self-management tool. Activity monitoring is likely to be most convenient for older adults when they can use accessible, commercial-grade monitors and cell phones. However, much remains unknown about how best to integrate these devices into behavioral interventions for specific groups of vulnerable older adults.

The goal of this study is to collect preliminary data regarding wearable monitor use by primarily African American older adults in Detroit in preparation for a trial of a community-based CBT intervention for chronic pain. Findings from the proposed study will inform the design of this future intervention, helping to ensure that it is effective and feasible in the Detroit community setting, and establishing a strong foundation for future competitive proposals. This is a high-priority population given the sharply disproportionate disease burden among older adults in Detroit and race disparities in pain treatment. Facilitators and barriers to activity monitor use in this population will be assessed and the feasibility and validity of various strategies for reporting daily step count data will be tested. This study is also known as the **STEPS (Seniors Tracking Exercise for Pain Self-management)**

## B. Specific Aims:

1. Identify 50 adults, predominantly African American, age > 60 years with chronic musculoskeletal pain. Thirty of these participants will be randomly assigned to receive a FitBit Zip™ and instructions for reporting daily step-count data in 3 ways (2 weeks each of manual via Interactive Voice Response (IVR) telephone calls, manual via SMS (text messaging), automatic (via syncing the device with an app) (n=30); or to a control group (n=20).
2. After a six-week monitoring period: a) compare step data collection adherence (days provided/days anticipated) among the three intervention modes, within and across subjects; b) assess the validity of manual step reports by comparing them with device-stored data; and c) compare changes in functional outcomes between monitoring and control groups.

## C. Methods

*Inclusion criteria:* Age  $\geq$  60 years, ambulatory with or without assistive device, community living; have a SMS-capable cell phone, Internet access (via smartphone, in-home or elsewhere); self-reported chronic musculoskeletal pain (pain in muscles or joints for  $\geq$  3 months);  $\geq$ 4 (1-10 scale) average pain level over last week;  $\geq$ 1 day/previous 30 when pain made it difficult to do usual activities. In addition, participants will have to be able to travel to a location in Detroit for a one-time study orientation session.

*Exclusion criteria:* serious acute illness or hospitalization in last month, planned surgery in next month or severe cognitive impairment.

*Recruitment strategies:* A total of 50 adults meeting above eligibility criteria will be recruited from the Healthier Black Elders Center Participant Resource Pool, an opt-in research registry available to UM researchers via the Pepper Center collaboration with Wayne State University. As of January 2017, the database included 1400 individuals with an arthritis diagnosis; many of these registrants are expected to meet pain-related study criteria. Secondary sources will include flyers and outreach at community locations serving Detroit seniors.

*Randomization and data collection:* After completing a baseline telephone survey, participants will be randomly allocated in a 2:1 ratio (intervention: control) using a computer-generated scheme to the monitoring condition or a no-monitoring control group. Participants in the intervention (monitoring) group will be invited to attend an orientation session in a central Detroit location where they will receive a FitBit Zip™ monitor and instructions in setting up their device and reporting data. A project hotline will be available for technical support. Participants will receive \$10 for each questionnaire completed and can keep FitBits upon study completion (control participants will receive FitBits after follow-up survey).

Participants will be asked on the follow-up survey whether they would like to be contacted in the future to learn about opportunities to participate in studies on this topic. They will be told that they will receive all current study incentives whether or not they wish to be contacted in the future, and that they can remove themselves from the “contact” list at any time.

*Intervention group:* Intervention group participants will monitor and report step count data daily for six weeks, after which they will complete a telephone follow-up survey. For the first two-week period, a random half of the intervention group participants will receive IVR calls and half SMS messages; for the second two weeks these groups will ‘switch’; and all intervention group participants will be asked to use the automatic sync feature for the final two weeks of the six-week period.

The commercially-available Fitbit Zip™ pedometer and activity tracker can be attached to the participant’s waistband, belt, shirt, or stowed in his/her pocket. The Fitbit wirelessly syncs data from the tracker to the Fitbit software, or through an app compatible with most smartphones. The software is free for download on both Macs and PCs. Study staff will provide the activity tracker at an orientation session and assist with downloading the software including creation of a study-specific user name for downloading step count data. The participant will be asked to not add identifiable information to the Fitbit site during the course of the study.

Participants will be instructed to wear their pedometer during waking hours, except showering, bathing, or swimming, every day throughout their enrollment in the study. At any time if the participant has questions regarding the use of the pedometer or problems uploading step counts, a study staff member can be contacted by phone to assist. Study staff will retrieve users’ step

count data in three different ways, using each mode for a 2-week period (for a total of 6 weeks wearing the Fitbit and reporting data) as described below:

- *Manual upload:* Participants will be asked to use the display on their FitBit to view and then manually input daily step counts via daily IVR calls they will receive at evening times convenient to them. If the initial IVR call is missed, the system will try again 15 minutes and one hour later. For the SMS mode, participants will designate the time of evening they would like to receive their daily text. A second text will be sent one hour later if there is no response to the first.
- *Automatic upload:* As described above, the research assistant will instruct participants in how to set up the FitBit so that data *automatically uploads* to the intervention website. Note that during this set-up process, the devices will be paired with a study account, and the email address provided will belong to the study. The information provided to the Fitbit company during set-up will not be identifying. It will include a study username, a masked birthdate (01/01/birth year plus or minus a constant), and a height and weight that is the male or female average, as appropriate.

*Control group:* Control group members will not track their steps during the study period, but will participate in baseline and follow-up data collection, after which they will receive a FitBit to keep.

Data collection:

Data will be collected via telephone by a trained research assistant at baseline and following the 6-week intervention.

Measures:

*Primary outcomes:*

Adherence to reporting will be indicated by the proportion of days with successfully logged step-counts, i.e., reported days/14 total days for each of the three reporting modes.

Pain interference: 4-item subscale from the PROMIS-29 Adult Profile, measured at baseline and follow-up.

*Secondary outcomes:*

Physical functioning: 4-item subscale from the PROMIS-29 Adult Profile, measured at baseline and follow-up.

Social participation: 4-item subscale from the PROMIS-29 Adult Profile, measured at baseline and follow-up.

Validity of manually-reported step counts will be assessed by comparing up to one month of IVR or SMS- collected data to data collected by syncing the device. Validity of the data will also be

assessed by examining associations between step data and relevant baseline characteristics (e.g., functioning scores, comorbidities, and age).

*Other baseline survey measures* (to characterize sample and/or as potential moderators of adherence and outcomes): *Demographics and health*: age, gender, education, race/ ethnicity, marital status, health literacy, comorbidities, cognitive functioning, physical activity. *Pain-related*: pain duration, number and location of pain sites, pain treatments, pain centralization. *Technology-related*: attitudes toward technology, eHealth literacy, social support for technology use.

*Staff burden*: Number of participant calls to the study technical support line, time spent giving technical assistance, and difficulties encountered as described in staff notes.

*Satisfaction/Acceptability*. In the follow-up survey, intervention group participants will be asked a series of Likert scale items about their experience with the trackers and reporting modes.

Open-ended items for intervention participants will assess challenges and facilitators for device and reporting method use; identify environmental and individual barriers to using devices; and obtain feedback on how program implementation might be improved for this particular population.

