#### Statistical Analysis Plan

Descriptive statistics will be calculated for baseline variables, comparing intervention and control groups using independent-sample t tests for continuous variables and chi-square tests for categorical variables, and on survey items related to satisfaction, acceptability, and adherence to step count reporting.

*Step data collection adherence:* (Days provided/14 days anticipated) among the three intervention modes, within and across subjects;

*Validity of manual step reports:* Proportion of days/21 days that manually-collected (SMS and IVR) and FitBit-stored counts are within 50 steps of each other will be calculated.

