#### *Functional outcomes*

Per the recommended scoring algorithm (see <https://www.healthmeasures.net/explore-measurement-systems/promis>), items in each PROMIS-29 subscale of Pain Interference, Physical Function, and Social Participation were summed and converted to a subscale T score, a standardized score with a population average of 50 and a standard deviation of 10. Means at baseline and follow-up of each subscale per treatment condition will be calculated.

Repeated measures analysis of variance (ANOVA) will be used to assess treatment effect: A time-by-treatment interaction term, indicating differential pre–post change by group, was the main predictor of interest.

We used chi-square tests to evaluate differences in the proportion of participants in intervention vs control groups who achieved the minimally important difference—that is, the smallest clinically relevant difference—of 3 T-score points in the PROMIS Pain Interference measure and in the proportion who increased the frequency and duration of their low-intensity walks from baseline to follow-up (vs decreased or stayed the same).

Qualitative data on satisfaction, barriers, and facilitators from open-ended survey responses will be compiled and detailed notes made from recordings of postprogram interviews and technical support logs. These were reviewed and coded, and all meaningful statements were placed by two researchers ([name]) into conceptual categories under the broad a priori themes of challenges/disadvantages and facilitators/advantages. In place of specialized software for qualitative analysis, we used standard word processing and spreadsheet apps.

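### Automatic sync is always used in weeks 5-6, so the three-mode adherence comparison cannot separate sync from time on study, and the SAP does not say so

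*Combined protocol and SAP*

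**What the plan says.** Under C. Methods (Intervention group), for the first two weeks "a random half of the intervention group participants will receive IVR calls and half SMS messages", and the two halves exchange modes for weeks 3-4. After that, "all intervention group participants will be asked to use the automatic sync feature for the final two weeks of the six-week period". There are therefore only two sequences: IVR-SMS-sync and SMS-IVR-sync.

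Aim 2a is to "compare step data collection adherence (days provided/days anticipated) among the three intervention modes, within and across subjects". C. Methods (Measures) lists adherence under primary outcomes, defined as "reported days/14 total days for each of the three reporting modes". The adherence line of the Statistical Analysis Plan reads "Days provided/14 days anticipated) among the three intervention modes, within and across subjects" and stops there. It names no model or test, and it does not mention period, order or time on study. Nothing limits what may be concluded about sync, and no reason is given for the fixed order. The only time term in the SAP is the time-by-treatment interaction, which belongs to the PROMIS outcomes.

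**The concern.** Every sync observation comes after four weeks of daily manual reporting, and every observation in weeks 5-6 is a sync observation. If the three proportions are set side by side as planned, a gap between sync and the manual modes may reflect the mode. It may equally reflect reporting fatigue, growing familiarity with the device, or participants having stopped by week 5. Fatigue or stopping would make sync look worse and practice would make it look better. The documents do not allow the direction to be predicted, so a reader cannot correct for it.

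This matters because of the study's stated use: "Findings from the proposed study will inform the design of this future intervention". Manual versus automatic reporting is an obvious choice for that later design, and it is the contrast this study cannot isolate.

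**Working it through.** The plan states no sample size calculation, effect size or adherence rate for this comparison, so there is no figure of its own to reproduce. The check is first of identifiability, then of size.

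**Inputs from the documents.** 30 monitoring participants (Aim 1); three two-week periods; two sequences, with sync always third (C. Methods).

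**Assumptions.** 15 participants per sequence; all 30 contribute all three periods; independent errors with equal within-person SD σ per period, σ = 0.20 to 0.30 on the proportion scale; a linear drift of s = 2, 5 or 10 percentage points per period that applies equally to all modes. The identifiability result does not depend on s or σ.

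**1. Identifiability.** Fixed participant effects (30 columns), period (2) and mode (2) give 34 columns. The period-3 and sync columns are identical, so the rank is 33.

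- Sync − IVR, sync − SMS and sync − manual mean: not estimable.
- SMS − IVR: estimable, variance 2σ²/30 = 0.0667σ².

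**2. Bias if time is ignored.** Sync sits at period 3 and the manual modes average period 1.5. The bias of sync − manual mean is therefore (3 − 1.5)s = 1.5s, in the direction of the drift. For SMS − IVR it is 0, because each mode falls equally in periods 1 and 2.

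**3. Precision if time is ignored.** Each participant's contrast has variance σ²(1 + ½) = 1.5σ², so the mean has variance 1.5σ²/30 = 0.05σ². The 95% half-width is t(0.975, 29) × σ × √0.05:

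- σ = 0.20: 9.1 points
- σ = 0.25: 11.4 points
- σ = 0.30: 13.7 points

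**4. Bias against precision.** Coverage of the nominal 95% interval is from the noncentral t with 29 df.

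| Drift per period | Size of bias | Days of 14 | Bias / half-width | Coverage at σ = 0.20 / 0.25 / 0.30 |
|---|---|---|---|---|
| 2 points | 3 points | 0.42 | 22-33% | 0.90 / 0.92 / 0.93 |
| 5 points | 7.5 points | 1.05 | 55-82% | 0.63 / 0.75 / 0.81 |
| 10 points | 15 points | 2.10 | 109-164% | 0.10 / 0.26 / 0.42 |

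**5. Can a time trend rescue it?** Only by assuming its shape. With linear time, the slope comes from periods 1 and 2 alone. Writing M1, M2, M3 for the period means, the estimate is M3 − (M1 + M2)/2 − 1.5(M2 − M1) = M3 + M1 − 2M2. Its variance is (1 + 1 + 4)σ²/30 = 0.20σ², which is 0.20/0.05 = 4 times the unadjusted variance. The half-width t(0.975, 57) × σ × √0.20 is 17.9, 22.4 and 26.9 points at σ = 0.20, 0.25 and 0.30. The data cannot test the linearity this relies on.

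**6. What the design does support.** For IVR versus SMS, with mode, period and sequence terms, the half-width is t(0.975, 28) × σ × √(2/30) = 10.6, 13.2 and 15.9 points.

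**The case against.** The study gathers preliminary data for a later trial. The SAP commits to no test, interval or decision rule on sync, so the half-widths and coverages above describe an interval nobody has promised to report. That is fair. It makes the harm one of misreading, not of a failed test. But Aim 2a says the modes will be compared, adherence is a primary outcome, and a purely descriptive table of three proportions is confounded in the same way.

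The size also rests on invented drifts and SDs, and on the drift carrying over to sync. Fatigue with answering an evening call or text need not affect automatic upload, whereas loss of device wear or withdrawal could. This stands: the figures illustrate a bias of unknown size and sign and do not predict it. The aliasing itself needs none of these assumptions.

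Device-stored counts will exist for part of weeks 1-4, because the validity analysis uses them. They could show whether wear changed over time. They do not measure adherence to sync as the assigned mode, and they do not make the sync contrasts estimable.

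Finally, a fixed order may have been practical. It may well have been, and the remedy does not require changing it.

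**Conclusion.** The concern holds. Under unrestricted period effects, the two comparisons involving sync are completely confounded with time on study, and no analysis of the planned data removes this without an untestable assumption about the shape of time. Under the stated assumptions the bias in sync minus the manual mean is 3 to 15 points. It exceeds the unadjusted half-width only at the 10-point drift, but nominal 95% coverage is already down to 63-81% at 5 points.

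The reach is limited. IVR versus SMS is unaffected by a period effect common to both sequences, and neither the validity check on manual counts nor the between-group pain interference outcome is touched. The plan should be corrected on this point, but the rest of the study stands.

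**What to change.** In the adherence paragraph of the Statistical Analysis Plan, state that:

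1. IVR versus SMS is the inferential mode comparison, analysed within participant as a two-period crossover over weeks 1-4, with mode, period and sequence terms and participant as the cluster. Use a random-effects or marginal model, since a sequence term is not estimable alongside fixed participant effects.
2. Sync adherence in weeks 5-6 is reported descriptively.
3. Any difference between sync and the manual modes is confounded with time on study and is not interpreted as a mode effect.

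Reword Aim 2a to match. A sync contrast adjusted for linear time may be added as a labelled sensitivity analysis, with its wider interval and the linearity assumption stated.

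Rotating all three modes through the periods would make every contrast estimable: with six sequences of five participants the matrix has full rank, 34 of 34, and each pairwise variance is 0.0667σ². That is open only if enrolment has not begun. The past tense under Functional outcomes ("We used chi-square tests to evaluate differences in the proportion of participants") makes this unlikely, so the revised text should also record when it was written relative to the data.

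The cost is wording in the SAP and in Aim 2a, with no new data or participants. The sponsor gives up an inferential manual-versus-automatic comparison that the design does not support.

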#### *Data Management Protocol*

A REDCap database will be set up to contain all participant data, including identifying information. After training regarding issues of confidentiality, only specially designated research staff will be authorized to have password-secured administrative access to the master list of names and original participant data. All other research staff and health educators will only have access to specific and select information on an “as needed” basis in order, e.g., to collect interview data, conduct the intervention or mail gift card incentives. This level of access will also be password secured to just those few individuals who need the data. Otherwise, participants’ data records will have only a sequential code number necessary for identification.

Data management personnel will prepare the data entry software, and will set up the logical and range checks. This software will store the data, together with the date of entry, in a data entry set that will be maintained in the research office at the School of Public Health.

Written documentation of data collection, storage, and transmission procedures will be maintained by the data management personnel.

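### Nothing masks the follow-up interviewer, whose role also sets up the devices, so interviewer knowledge and rapport could affect a self-reported primary outcome differently by arm

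*Combined protocol and SAP*

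**What the plan says.** **Outcome.** The Measures part of section C lists, under primary outcomes, "Pain interference: 4-item subscale from the PROMIS-29 Adult Profile, measured at baseline and follow-up". Physical functioning and social participation, from the same instrument, are secondary.

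**Who collects it.** The Data collection paragraph says: "Data will be collected via telephone by a trained research assistant at baseline and following the 6-week intervention".

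**Who handles the devices.** The automatic-upload item in section C says "the research assistant will instruct participants in how to set up the FitBit". The intervention-group text adds "Study staff will provide the activity tracker at an orientation session and assist with downloading the software", and for later problems "a study staff member can be contacted by phone to assist". For controls, section C describes only the two surveys, followed by a device once follow-up is done.

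**What else is in the follow-up survey.** Under Satisfaction/Acceptability, "intervention group participants will be asked a series of Likert scale items about their experience with the trackers". Open-ended items for the same arm follow. The order of the survey is not given.

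**Timing and analysis.** Randomization follows the baseline telephone survey. Under Functional outcomes, the SAP tests pain interference in two ways: by the time-by-treatment interaction in a repeated measures ANOVA, and by a chi-square comparison of the proportions achieving a 3-point T-score difference.

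**Access to data.** The Data Management Protocol says "All other research staff and health educators will only have access to specific and select information". That rule serves confidentiality and does not mention allocation.

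**The concern.** Participants answer the PROMIS items themselves, so the interviewer rates nothing. An interviewer can still influence answers through tone, prompting and the relationship with the respondent. Here the interviewer belongs to the role that trains one arm on its device, and nothing prevents the caller from knowing the arm before the PROMIS items are asked. If tracker questions come first, they disclose the arm to any caller.

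At stake is the between-arm comparison of pain interference and of the two secondary PROMIS scores. A baseline taken before allocation cannot correct an influence that begins after it. Participants will always know whether they wore a tracker, so their own expectation cannot be removed. The interviewer's part can be reduced, and the plan does not attempt it.

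**Working it through.** The plan states no power, alpha or bias figure, so there is nothing to reproduce. The check has two parts.

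**1. Reading the sections together**

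- Collector of the outcome and trainer on the device: the same role title, both in section C. The text does not say whether they are the same individual.
- Staff contact between baseline and follow-up: orientation and optional phone help in the intervention arm; none described for controls.
- Masking, a separate assessor or withheld allocation: not mentioned in section C, in the data security and management sections or in the SAP.
- Order of items in the follow-up survey: not stated.

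**2. Where a reporting shift would go**

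Let δ_I and δ_C be the average follow-up reporting shifts in the intervention and control arms, each counted as positive towards improvement. Baseline reports are made before allocation, so they carry no systematic arm difference. Then:

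expected difference in change = true effect + b, with b = δ_I − δ_C.

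This is the quantity that the time-by-treatment term estimates, so b is not cancelled. It has a participant part (knowing one's own arm) and an interviewer part (knowledge and rapport). Only the second can be reduced.

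**Illustration of scale**

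From the documents: 30 and 20 participants (Specific Aims), T-score SD 10 and a 3-point threshold (SAP). Assumed: a two-sided 5% test, pre–post correlation r of 0.5 to 0.7, b of 1 to 3 points, no true effect, and normally distributed change.

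- SD of change = 10 × √(2(1 − r)) = 10.0 at r = 0.5 and 7.75 at r = 0.7.
- SE = SD of change × √(1/30 + 1/20) = 2.89 and 2.24.
- P(reject) = Φ(b/SE − 1.96) + Φ(−b/SE − 1.96).
- P(improvement of 3 or more) = Φ((b − 3)/SD of change). Here the whole of b is placed in the intervention arm for simplicity.

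| b (points) | b as share of 3 points | P(reject), r = 0.5 | P(reject), r = 0.7 | Reaching 3 points, r = 0.5 | Reaching 3 points, r = 0.7 |
|---|---|---|---|---|---|
| 0 | 0% | 5.0% | 5.0% | 38.2% | 34.9% |
| 1 | 33% | 6.4% | 7.3% | 42.1% | 39.8% |
| 2 | 67% | 10.7% | 14.5% | 46.0% | 44.9% |
| 3 | 100% | 18.0% | 26.9% | 50.0% | 50.0% |

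Section C gives the allocation as 2:1, which for 50 people is about 33 and 17 rather than 30 and 20. With 33 and 17 the rejection rates are 6.3–7.2%, 10.3–13.9% and 17.1–25.4% for b of 1, 2 and 3, so the picture does not change.

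**The case against.** The strongest reply is that participants know their arm, the items are self-reported and sum-scored, and so most of any reporting bias would remain even with a masked caller. This stands as a limit on what the fix can achieve. The figures above describe a total shift b, not the part that masking would remove.

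Several stronger readings are tempting, and the documents do not support them:

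- **That the caller has personally coached the participant.** Section C shows a shared role title, not a shared person. Elsewhere it says only study staff, and phone help is given when a participant asks. The Data Management Protocol lists interviewing and delivering the intervention as separate purposes for access, so separate people are possible. The plan permits overlap but does not establish it.
- **That only intervention answers can shift.** Controls also know their allocation and receive their device only after the follow-up survey, so disappointment or anticipation could move their answers. Both arms also speak to a research assistant at baseline.
- **That the bias must favour monitoring.** Courtesy to a helper makes this plausible. But the plan itself provides a hotline and asks about difficulties and barriers, and frustration with the device could work the other way.
- **That the survey order is wrong.** The questionnaire is not part of the documents. The order is unspecified, not shown to be bad.

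It can also be said that this is a 50-person preliminary study in which the functional comparison is the last of three sub-aims. That lowers the urgency. Pain interference is nevertheless named as primary and compared between arms, and the findings are meant to inform a later trial.

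**Conclusion.** The point holds as a gap in the safeguards around a subjective primary outcome. As written, the plan allows an unmasked research assistant, possibly one who trained the participant on the device, to collect pain interference and the two secondary PROMIS scores at follow-up. Any resulting difference between arms would pass straight into the interaction test, and could also alter the responder comparison.

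The size cannot be derived from the documents. Under the stated assumptions, a net shift of 1 point barely matters (6–7% false positives against 5%), while 2 points would matter (about 11–15% with 30 and 20). Neither shift is evidenced, and each mixes participant and interviewer effects. Towards benefit is the plausible direction, not a certain one.

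Reporting adherence, the other primary outcome, is logged by IVR, SMS or sync and compared within the intervention arm, so it is unaffected. This is a cheap improvement to make, not a defect that invalidates the study.

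**What to change.** 1. Put the PROMIS items first in the follow-up call, before any tracker, satisfaction or open-ended item, and ask participants at the start not to mention devices until told to.
2. Withhold the arm field in REDCap from the follow-up interviewer until the PROMIS section is locked. The planned role-based access could be extended to do this, but it was written for confidentiality, so the allocation rule must be added explicitly.
3. Where existing staffing allows, assign the call to a team member who did not run that participant's orientation or support calls. Step 2 masks only such a caller: hiding a field does nothing for someone who set up the participant's tracker. Where this is not possible, record that the interviewer was unmasked and report it as a limitation.

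The cost is a survey order, a permission setting and some loss of scheduling flexibility. The documents do not give the number of research assistants, so whether step 3 is always feasible is unknown; step 1 needs no extra staff. Parts of the SAP's Functional outcomes section are in the past tense. If the follow-up calls are already complete, the sponsor should instead state who interviewed whom, the item order used, and the resulting limitation.

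### Does the adherence score (reported days out of 14) need a written rule for step counts that arrive late?

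*Combined protocol and SAP*

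**What the plan says.** Section C, Measures, defines the outcome as the "proportion of days with successfully logged step-counts, i.e., reported days/14 total days for each of the three reporting modes". Aim 2a in section B sets the comparison for the end of the six-week period: "compare step data collection adherence (days provided/days anticipated) among the three intervention modes, within and across subjects". The Statistical Analysis Plan repeats it as "Days provided/14 days anticipated) among the three intervention modes, within and across subjects". None of the three gives a time limit for a day's count.

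On the participant's task, section C states: "Intervention group participants will monitor and report step count data daily for six weeks". IVR calls are retried after 15 minutes and after one hour. An unanswered text gets one reminder an hour later. These are contact schedules and do not say how a day is scored.

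On access, a participant must "have a SMS-capable cell phone, Internet access (via smartphone, in-home or elsewhere". On the sync route: "The Fitbit wirelessly syncs data from the tracker to the Fitbit software, or through an app compatible with most smartphones", and "The software is free for download on both Macs and PCs". Sync is the mode for everyone in weeks five and six. The technology items in the baseline survey are "attitudes toward technology, eHealth literacy, social support for technology use"; type of Internet access is not among them.

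**The concern.** The three modes handle lateness differently. An IVR call has a last described attempt one hour after the first, so a missed evening is normally lost. A sync can deliver earlier days: the validity analysis relies on this when it sets up to a month of manual reports against counts obtained by syncing. One label, reported days out of 14, could therefore mean same-evening reporting for IVR and eventual capture for sync.

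Eligibility makes late uploads foreseeable. Someone with neither a smartphone nor a home connection can sync only where there is a connection, and days between visits arrive late.

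The score by mode is a primary outcome meant to shape a later intervention, and the background section values monitors for the timeliness of their data. If late days count, a high sync score does not show timely arrival. If they do not, a low score partly reflects where people have Internet. A reader who did not know the rule could not tell which.

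**Working it through.** The plan states no sample-size, power or precision figure for adherence, so there is nothing of its own to reproduce. The check is day counting.

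**Inputs from the documents.** 14 days per mode; 30 intervention participants.

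**Assumptions (not in the documents).** A participant wears the device daily and syncs every k days, first on day j (j = 1 to k). The tracker stores at least k days. The other participants sync daily and score 100%.

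**One participant.**
- Same-day credit = number of syncs / 14.
- Credit by day 14 = day of last sync / 14.
- No cut-off = 14/14.

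| Sync interval | Same-day credit | Credit by day 14 | No cut-off |
|---|---|---|---|
| Daily | 100% | 100% | 100% |
| Every 2 days | 7/14 = 50% | 13/14 to 14/14 = 93–100% (mean 96.4%) | 100% |
| Every 3 days | 4/14 to 5/14 = 29–36% (mean 33.3%) | 12/14 to 14/14 = 86–100% (mean 92.9%) | 100% |
| Weekly | 2/14 = 14% | 8/14 to 14/14 = 57–100% (mean 78.6%) | 100% |

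The strictest rule drives the contrast. With weekly syncs on days 7 and 14, a grace of 1, 2 or 3 days gives 4/14, 6/14 or 8/14, that is 29%, 43% or 57%. Shorter storage lowers the late-credit figure: 3 days gives 6/14 = 43% and 5 days gives 10/14 = 71%.

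**Mean of 30: same-day credit against credit by day 14.** Shift in points = 100 × (m/30) × difference between the two scores, for m infrequent syncers. Averaged over j, for intervals of 2, 3 and 7 days:
- m = 0: no shift.
- m = 3: 4.6, 6.0, 6.4.
- m = 6: 9.3, 11.9, 12.9.
- m = 9: 13.9, 17.9, 19.3.

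Without averaging, weekly syncing with m = 3 runs from 100 × 0.1 × 6/14 = 4.3 (first sync on day 1) to 100 × 0.1 × 12/14 = 8.6 (first sync on day 7).

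**Mean of 30: credit by day 14 against no cut-off.** This is all that stays open if days provided means any day eventually held. For weekly syncing the average shift is 100 × (m/30) × (14 − 11)/14, which is 2.1 points for m = 3, 4.3 for m = 6 and 6.4 for m = 9. For syncing every 2 days with m = 6 it is 100 × 0.2 × 0.5/14 = 0.7.

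**Scale.** The 95% half-width of a paired mode difference with n = 30 is t(0.975, 29) × SD/√30. With an assumed SD of 0.2 this is 2.045 × 0.2/5.477 = 0.075; with 0.4 it is 0.149. That is 7.5 to 15 points.

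**Which rule the text supports.** Aim 2a and the SAP count days provided, and the aim places the comparison after the monitoring period. Measures counts days with a logged count. The validity analysis expects counts to be fetched later by syncing. In the sync mode the upload is meant to happen without a nightly act by the participant. The instruction to report daily describes the task; no section turns it into a condition for crediting a day.

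**The case for a change.** The best case for a change is that the gap is in a primary outcome and cheap to close, and that it separates modes Aim 2a sets side by side. Reporting is described as daily, and IVR has in effect a same-evening window while sync has none. The issue reaches anyone who syncs less than daily, whatever their Internet access. If 6 of 30 did so, the choice between the two extreme rules would move the sync mean by 9 to 13 points on average, comparable with the precision of the comparison.

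The asymmetry stands: IVR and sync scores do not measure the same promptness. The rest is weaker.
- The 14% needs a rule that no section states.
- Access outside the home need not be infrequent, and the documents do not say how many people have only that.
- Access problems would not go unseen: the follow-up survey asks about barriers in participants' surroundings, and staff log difficulties and support calls.
- Since feasibility in this population is the purpose, a sync score lowered by poor access is partly the result sought.
- Separate timely and eventual figures would need sync upload times, which the plan does not describe keeping. Without them, the eventual figure is the only one available.
- Sync is always the last period, so its contrast with the manual modes is confounded with period under any rule.

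**Conclusion.** No change is needed. The plan does omit an arrival cut-off, but its wording leads an analyst to a sound score: days for which a count is held, out of 14. On that reading the remaining freedom is whether uploads after day 14 count, worth on average about 2 to 6 points on the sync mean if 3 to 9 of 30 sync weekly, less if they sync more often, and nothing if nobody syncs late. Those averages lie below the 7.5 to 15 point half-width of a paired difference, though a single weekly pattern starting on day 1 would double them.

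These sizes rest on an assumed sync interval, number affected, storage length and SD. No direction of bias is shown. The study is preliminary, and the SAP sets no test or threshold for adherence that the choice could tip. The sync result should be read as eventual capture.
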